**(If Applicable):**

**RESPONSIBLE ADVISOR:**

E-MAIL ADDRESS:

TELEPHONE:

DEPARTMENT:

ADDRESS (MSC):

**Investigator: Please respond to the questions below. The IRB will utilize your responses to evaluate your protocol submission.**

1.  YES  NO Does the James Madison University Institutional Review Board define the project as **research**?

The James Madison University IRB defines "research" as a "systematic investigation designed to develop or contribute to generalizable knowledge." All research involving human participants conducted by James Madison University faculty, staff, and students is subject to IRB review.

2.  YES  NO Are the human participants in your study **living** individuals?

"Individuals whose physiologic or behavioral characteristics and responses are the object of study in a research project. Under the federal regulations, human subjects are defined as: living individual(s) about whom an investigator conducting research obtains: (1) data through intervention or interaction with the individual; or (2) identifiable private information."

3.  YES  NO Will you obtain data through **intervention** or **interaction** with these individuals?

"Intervention" includes both physical procedures by which data are gathered (e.g., measurement of heart rate or venipuncture) and manipulations of the participant or the participant's environment that are performed for research purposes. "Interaction" includes communication or interpersonal contact between the investigator and participant (e.g., surveying or interviewing).

4.  YES  NO Will you obtain **identifiable private information** about these individuals?

"Private information" includes information about behavior that occurs in a context in which an individual can reasonably expect that no observation or recording is taking place, or information provided for specific purposes which the individual can reasonably expect will not be made public (e.g., a medical record or student record). "Identifiable" means that the identity of the participant may be ascertained by the investigator or associated with the information (e.g., by name, code number, pattern of answers, etc.).

5.  YES  NO Does the study present **more than minimal risk** to the participants?

"Minimal risk" means that the risks of harm or discomfort anticipated in the proposed research are not greater, considering probability and magnitude, than those ordinarily encountered in daily life or during performance of routine physical or psychological examinations or tests. Note that the concept of risk goes beyond physical risk and includes psychological, emotional, or behavioral risk as well as risks to employability, economic well-being, social standing, and risks of civil and criminal liability.

### **Background:**

Over 60% of patients who have a stroke will experience secondary problems with their swallowing (dysphagia) (Mann et al., 1999). However, at least half of acute stroke patients will discharge to home with limited follow up on their swallowing problem (Howrey et al., 2011), which can lead to severe consequences. Similar problems with need for continued access to swallowing therapy occur following treatment of head and neck cancer where patients usually experience swallowing difficulties following chemoradiation and surgery (Hutcheson et al., 2012; Hutcheson & Lewin, 2012). Patients with swallowing disorders following traumatic brain injury also usually require a prolonged period of rehabilitation (Hansen et al., 2008). Once patients are discharged to home, limited access and cost issues are often barriers to continuing swallowing rehabilitation and consequently the patient's swallowing problem is chronically untreated. This not only negatively impacts the patient's quality of life and their ability to eat an oral diet, it fails to address chronic aspiration that can lead to rehospitalization and death. Continuing dysphagia care immediately following discharge is extremely important as earlier treatment leads to better outcomes (Odderson et al., 1995).

We are currently developing the Passy Muir Swallowing Self-Trainer to continue treatment of dysphagia after the patient is discharged to home. The self-training device is worn around the neck with motors placed externally on the skin over the thyroid cartilage to provide vibratory stimulation to the larynx (Figure 1). The vibrations activate the sensory receptors inside the larynx which excite CNS control for swallowing (Chi-Fishman, 1994) and can help the patient to initiate swallowing. Patients can use the self-training device at home to promote swallowing rehabilitation during daily swallowing practice. The device can also be programmed to vibrate at regular intervals throughout the day to promote saliva swallows. Using this method, the patient can continue their swallowing therapy independently and in a manner that is cost effective. A previous Phase I trial compared the clinical outcomes of 8 patients with chronic dysphagia using either an intramuscular electrical stimulation implant device or an external vibratory stimulator to practice swallowing daily at home (FDA IDE GOG0153). Functional outcomes of oral intake improved with both devices. As the external vibratory stimulation has the advantage of being external and completely noninvasive, it has been selected for further development as a self-training device. A second pilot study (IRB-

12-0057) examined the effect of different frequencies of vibration on the swallowing frequency of healthy participants and found swallowing significantly increased from baseline when using a vibration of 70 Hz on one side of the larynx and 110 Hz on the other side (Figure 2). Data is currently being collected on the effect of different vibration characteristics on swallowing in participants who have swallowing problems after stroke (IRB-13-0010).

**Purpose:** The purpose of this study is to allow patients with chronic dysphagia to use the Self-Trainer for daily swallowing practice in their home and collect feedback on device use and satisfaction and use. Objective information on the effectiveness of self-training for swallowing rehabilitation will also be gathered.

### **Objectives:**

1. To develop and evaluate training for participants and caregivers to use the self-trainer.

[figure not shown]

Figure 1. The Passy-Muir Swallowing Self-Training device is worn around the neck with the motors making contact with either side of the thyroid cartilage. These motors vibrate to stimulate the sensory nerves that induce swallowing.

[figure not shown]

Figure 2: the 70/110 Hz motor increased swallowing by 100% or more in all healthy

2. To gather participant feedback on the use of the device after 3 months of daily practice.
3. To determine how 3 months of daily practice with the Passy Muir Swallowing Self-Trainer affects swallowing physiology, brain activation, oral intake, and quality of life in participants with chronic dysphagia.

### **Procedures/Research Design/Methodology/Timeframe**

Design: This study is a case series study of participants using the device to evaluate patient preferences such as frequency of device use, compliance with training guidelines, patient and caregiver training required for appropriate use, and patient and caregiver feedback on satisfaction with the device. All participants will continue any outpatient rehabilitation they are receiving during this time period. This research will determine device training and use parameters before designing a Phase II controlled trial of the degree of benefit from device use. All participants and their caregivers will be trained on correct use of the Swallowing Self-Trainer and will use the device to practice swallowing in their home environment for 3 months (months 1-3). Each participant will complete the outcomes measures at baseline and immediately after the 3 months of device use.

Subjects: Between 12 and 20 participants with oropharyngeal swallowing problems will be recruited from the local area for participation. Participants must be 13 years of age or older. Parental consent will be obtained simultaneous to participant consent if the participant is under 18. Recently the principle investigator was contacted by the speech pathologist of a minor who has had a stroke and dysphagia and is interested in participating in this study.

Recruitment: Participants will be recruited from community hospitals, rehabilitation centers, and home health services in the local area. Participants who have previously participated in the protocol, The Passy Muir Swallowing Self Training Device to Enhance Recovery Post Stroke (13-0010), and have documented during the consent process that they will wish to be contacted with information on future studies will also be recruited to participate in this study.

Each participant will be given \$20 for each visit they attend at Sentara RMH Medical Center (SRMH) for training or data collection purposes and \$100 upon completion of the study. Travel mileage will also be reimbursed. All study compensation will be given in the form of a check mailed to the participant to the address they have specified by the study sponsor, Passy Muir. Hotel stay can be arranged and paid for if the participant is required to stay in Harrisonburg overnight. Hotel stay will also be paid for by the study sponsor, Passy Muir.

Documentation of Dysphagia: Participants will be identified as having swallowing difficulties for admittance into the study by obtaining medical records. Swallowing difficulty will be verified during the modified barium swallow completed as a baseline outcome measure.

Exclusion criteria: Exclusion from this study is contingent on participant self-report of one of the following:

- Ongoing psychiatric disorder for which the patient is receiving medication and is under the care of a psychiatrist
- Epileptic seizure
- Severe speech or language problems affecting communication and reading comprehension
- Cognitive impairment limiting understanding of the consent process and ability to follow directions as assessed by the Folstein Mini-mental State Examination (Folstein et al. 1975) with a score of less than 23.
- Diagnosis of esophageal disorders interfering with the ingestion of food and/or liquid.
- Inability to tolerate a nasal endoscopic exam.
- Rapidly progressive neurological disease such as amyotrophic lateral sclerosis, myasthenia gravis, and progressive supranuclear palsy.

Inclusion criteria:

- Participant must be 13 years old or older
- If the participant is under 18, parental consent must be given

- Stable medical condition
- Diagnosis of oropharyngeal dysphagia confirmed by MBS baseline measure of the following two scales:
  - Penetration-Aspiration Scale score of 2 or greater verified by modified barium swallow (Rosenbek et al., 1996; Appendix I) and/or
  - Functional Oral Intake Scale score of 5 or lower (Crary et al., 2005; Appendix P)
- Folstein Mini-Mental State Examination (MMSE) score of 23 or greater indicating cognitive ability to follow directions and communicate preferences (Appendix H)
- Willingness to travel SRMH2 or more times to undergo initial evaluation, device use training and checkup at 3 months.

Exclusionary Criteria for Participants Who Agree to Undergo MRI and fNIRS:

- Pregnancy
- Cardiac problems
  - history of cardiac rhythm condition (including heart murmur or cardiac arrhythmia)
  - cardiac pacemaker in place
- Highly-pigmented (dark) skin color is an exclusion criterion because near-infrared spectroscopy requires the measurement of the degree of absorption of different wavelengths of light after being reflected back through the scalp. Highly pigmented skin interferes with wavelength transmission, making the measurement of changes in absorption inaccurate.
- Lack of a primary care physician who can be contacted if there are findings on the MRI.
- Presence of metal in the body (prostheses, electrodes, shrapnel, aneurism clips, other medical hardware)
- Presence of certain tattoos with ferromagnetic metal or permanent makeup, due to the exposure to high magnetic force through MRI procedures.
- Subjects who were metal workers as a previous occupation will also be excluded due to the possibility of unknown/undetected metal in their body.
- Volunteers with broken skin in the area that the fNIRS probes will be placed on the scalp
- Claustrophobia
- Previous surgery that used surgical staples
- Artificial joints

Will data be collected from or about any of the following populations?

Minors (under 18 years of age); Specify Age: 13 and over  
 Prisoners  
 Pregnant Women  
 Fetuses  
 Cognitively impaired persons  
 Other protected or potentially vulnerable population  
 Not Applicable

Passy-Muir Swallowing Self-Trainer

The Self-Trainer is designed to be used in either automatic or manual mode. The mode can be easily set using a switch on the side of the controller. When the controller is in automatic mode, the device will vibrate up to 15 seconds every 3-5 minutes. These specifications are set by connecting the Self-Trainer to a computer terminal by the investigators. When the controller is in manual mode, the device operates in a momentary manner, specifically the device only vibrates when the button is pushed.

Swallow Practice

[figure not shown]
The participant will practice swallowing with the Self-Trainer daily in their home environment for 3 months. The Self-Trainer device will be set to vibrate at a vibration rate and pressure that is ideal for each participant based on testing (see Procedures Part B, section g). The participant will wear the Self-Trainer during waking hours with the device in automatic mode. In automatic mode the Self-Trainer will be programmed to vibrate up to 15 seconds every 3-5 minutes to stimulate saliva swallows and promote swallowing practice. In this manner the participant will complete approximately 180-300 saliva swallows per day.

The participant will also engage in 30-60 minutes of active swallowing practice every day by switching the device to manual mode and manually pushing the button to turn on the vibration while swallowing, and releasing the button to turn off the vibration. The participant will complete a total of 60 practice swallows a day by doing 30 trials of practice 2 times a day. Participants will be given a small 5 cc syringe or  $\frac{1}{4}$  teaspoon for administering 1-2 cc of water (equivalent to a saliva swallow) to moisten their mouths during each of their practice swallows.

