intake. As a screening test, the DOSS will be completed by the speech pathologist per discussion with the participant about their current oral intake (Appendix J). This rating scale form will be identified only by ID number with no personal health information. Each participant must obtain a score of 5 or lower, indicating a restricted diet secondary to oropharyngeal dysphagia, to participate in the protocol.

- f. Consented subjects will fill out the Edinburgh Handedness Inventory (Appendix O), a 10 question survey, to determine hand dominance.
- g. Self-Trainer Motor Selection: If the participant has participated in the protocol "The Passy Muir Swallowing Self-Training Device to Enhance Recovery Post Stroke" (IRB 13-0010) then the optimal motor settings for the participant from this study will be used. However, if the participant has not participated in the previous study, then optimal motor settings will need to be identified for that patient. Motors at frequencies ranging from 30-150 Hz and other hybrid motors combining two frequencies (using 2-6 kPa neck pressure) will apply 8 seconds of stimulation followed by 15 seconds of rest for a total of 28 stimulation trials for a total of 10.7 minutes per motor frequency. Using the same vibration time specifications, neck pressure, vibration mode, and vibration duration may also be tested so that optimal motor parameters can be selected for each participant. Online recordings of bi-axial accelerometry of laryngeal motion and inductive plethysmography of respiration will identify laryngeal movement and respiratory apnea to confirm swallows. The rate of swallowing during the 10.7 minute condition will be computed for each motor condition and compared to baseline to identify the optimal motor to use with the patient for daily swallowing self-training during device use. All testing done for motor selection will be video recorded for later analysis. Each digital video file will be saved using the participant's study ID only and will be stored on an encrypted drive for 5 years after publication, after which it will be destroyed.

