- d. Modified Barium Swallow study (MBS) will be completed in radiology and requires the participant to swallow small amounts of barium. This will be done by a licensed speech-language pathologist who has been trained to complete MBS. An MBS study will be completed at baseline and after the 3 month self-training period. During each exam the participant will swallow thin liquid, nectar thick liquid, honey thick liquid, puree, and solid texture (cracker/cookie). For the entire MBS protocol, see Appendix L. The participant will be given each consistency in gradually increasing amounts from 5 ml to approximately 15 ml (See Human Subjects Protection). If more than a trace amount of aspiration is observed on any trial, the remaining trials of that consistency will be discontinued from the study. Radiation exposure time for each study will be 5 minutes or less. All MBS studies will be recorded for later analysis. All recordings will be de-identified with a random ID number. Each MBS study will include a 19 mm metal sphere calibration marker be taped to the side of the neck for future displacement measures. Each video will be analyzed for:
  - i. Modified Barium Swallow Impairment Profile score (MBSImp) (Martin-Harris et al., 2008) allows the speech pathologist to rate specific physiological movement during each swallow and assign an overall 0 to 55 numerical score representative of swallowing impairment in the oral, pharyngeal, and esophageal phase (Appendix L).
  - ii. Dysphagia Outcome and Severity Scale (DOSS) (O'Neil et al., 1999) allows the speech pathologist to assign a 1 to 7 numerical score to the safest food and liquid consistency that the participant can take orally, ranging from no food restrictions to no oral intake. The DOSS will be completed by the speech pathologist while reviewing each MBS while participant ID and condition will be masked (Appendix J). This rating scale form will be identified only by ID number with no personal health information.

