#### Human Subjects Protection

##### A. Potential Risks

During this case series, the participants are asked to wear the swallowing Self-Trainer around their neck to provide vibratory stimulation to the nerves that influence swallowing. They will wear the device during waking hours and prior research has shown that the stimuli can increase the frequency of swallowing 2-3x their normal rate. Participants will be instructed to only take food or liquid consistencies by mouth for nutritional purposes as recommended by the SLP based on their modified barium swallow while the device is on for swallowing training. Rather, the participants will swallow their own saliva or an equivalent amount of water (1-2 ml) as a part of the self-training, as they do on a normal basis throughout the day. As the most persons use up their saliva after 3 swallows, participants will be given a small syringe or ¼ teaspoon for administering 1-2 ml of water, equivalent to a saliva swallow, to moisten their mouths while practicing.

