For participants who take food orally these consistencies must be approved by the SLP as being safe to use with the device. If the participant is not safe for any intake, instructions will be given to remove the device from the participant's neck prior to food consumption they take for pleasure. As the Self-Trainer is known to increase the frequency of swallowing, the participants will be swallowing their secretions more frequently and therefore it is possible that each participant's risk of aspirating could change. For some participants, specifically those who do not swallow their secretions and instead periodically expectorate, the participant is now attempting to swallow the secretions instead of attempting to clear them from their oropharynx using regurgitation. Participants who do not feel secretions pooling in their throat may have a decreased risk of aspirating secretions while using the device as they are now prompted to swallow. As saliva swallows and the risks associated with saliva aspiration are an ongoing daily risk for these participants, this study provides only a minimal increase in risk. Efforts will be made to minimize any risk associated with participation in this study (see Protection against risks). If a participant expectorates their saliva as a part of reducing aspiration risk, they will be encouraged to continue with this practice as needed, but to try to swallow when they feel the urge to swallow as part of the self-training. The study will be conducted by a licensed speech language pathologist who will counsel each participant on minimizing secretion aspiration risk.

Participants will be encouraged to continue with their current swallowing treatment plan of care as determined by their speech language pathologist. We will take great care to make certain that all participants and their family and caregivers do not misinterpret the purpose of this research and fully understand that this study is experimental research with no guarantees of benefit. It will be made clear in the advertising material, informed consent and in any discussions with the participants and family members that treatment received is experimental research and there is no guarantee of improvements in swallowing function. The speech language pathologist conducting the research will provide participants and their

caregivers with referrals to patient services in their area for treatment of their swallowing disorder if appropriate.

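### Practice water is supplied for each of 60 daily home swallows without a recorded clinician decision for participants unsafe on thin liquid or on any intake

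*Protocol*

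**What the plan says.** Swallow Practice asks for 30 practice trials twice a day, 60 swallows in all, at home for 3 months. Participants press the button so that the device vibrates during each swallow. They receive a 5 cc syringe or a quarter teaspoon for "administering 1-2 cc of water (equivalent to a saliva swallow) to moisten their mouths during each of their practice swallows". No subgroup is excepted.

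Section A, Potential Risks, explains the water: "As the most persons use up their saliva after 3 swallows, participants will be given a small syringe" or spoon for "administering 1-2 ml of water, equivalent to a saliva swallow, to moisten their mouths while practicing". The same section lets participants take food and liquid for nutrition with the device on only as the SLP recommends from the barium swallow. It then sets practice apart from this, as swallows of saliva or an equal small amount of water. Section C, Protection against risk, allows saliva swallows or 1-2 ml of water as needed.

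Entry has no limit at the severe end. One criterion is a "Penetration-Aspiration Scale score of 2 or greater verified by modified barium swallow", and/or a Functional Oral Intake Scale score of 5 or lower. For the Dysphagia Outcome and Severity Scale, which extends to no oral intake, "Each participant must obtain a score of 5 or lower, indicating a restricted diet secondary to oropharyngeal dysphagia". Section A foresees the extreme case: "If the participant is not safe for any intake, instructions will be given to remove the device" before food taken for pleasure. Section C mentions participants fed through a PEG or nasogastric tube.

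Item 5 of section C forbids using the device with oral intake for which the participant is unsafe. Its next sentences speak only of food consistencies and of food in the mouth.

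**The concern.** Food and liquid taken for nutrition with the device on go through the SLP, and a participant who is unsafe on everything removes the device before eating. The practice water is swallowed with the device on, and nothing says who decides whether a given participant should have it.

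The reasoning in section C is that participants already swallow, and may aspirate, their own saliva all day, tube-fed or not. That covers saliva already present. It does not cover fluid added for someone who takes nothing by mouth. Nor does it cover the participants described in section A who spit out their secretions and are encouraged to go on doing so as needed.

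What is at stake is a safety instruction for the most impaired participants and a consistent definition of the intervention. No sample size, alpha level or endpoint is involved.

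**Working it through.** **Inputs.** 30 trials, 2 times a day, and 1-2 cc per swallow (Swallow Practice); saliva used up after about 3 swallows (section A); water as needed (section C); barium boluses from 5 ml to about 15 ml (D. Outcome measures, item d). Assumption: 3 months = 90 days.

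**The plan's own figure.** 30 × 2 = 60 practice swallows a day, as stated.

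**Water per participant under each wording.**

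- *Swallow Practice as written:* 60 × 1-2 ml = 60-120 ml a day. Over 90 days: 60 × 90 = 5,400 water swallows, 5.4-10.8 L.
- *Section A, if the first 3 swallows of each session use saliva and the rest use water:* (30 − 3) × 2 = 54 water swallows and 54-108 ml a day. Over 90 days: 54 × 90 = 4,860 water swallows, 4.86-9.72 L.
- *Sections A and C, if the participant chooses saliva or needs no water:* 0 ml.

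The range is therefore 0 to 60-120 ml a day, and 5.4-10.8 L is the top of it.

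**Item 5 against the practice instruction, for a participant unsafe on thin liquid.**

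- *Item 5 read literally:* water is oral intake, so the device may not be used with it. Swallow Practice supplies it for every device-assisted practice swallow. The two conflict.
- *Item 5 read as a rule about food, as its later sentences suggest:* the practice water falls outside it, and no other sentence assigns the decision to anyone.

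**What the baseline barium swallow contributes.** Thin liquid is tested: "During each exam the participant will swallow thin liquid, nectar thick liquid, honey thick liquid, puree, and solid texture". There is also a stopping rule: "If more than a trace amount of aspiration is observed on any trial, the remaining trials of that consistency will be discontinued". The smallest bolus described is 5 ml, which is 5/2 = 2.5 to 5/1 = 5 times the practice volume. Aspiration at 5 ml or more is a reason to ask whether 1-2 ml is acceptable; it does not answer the question. No sentence links this result to the practice water.

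**The case against.** The strongest reply is that the water was considered. Three places in the protocol call it equivalent to a saliva swallow, section A separates it from nutritional intake, and section C rests its minimal-risk statement partly on it. That is a disclosed clinical choice put before the IRBs, and nothing in the documents shows 1-2 ml of water to be more dangerous than saliva. This stands as far as it goes: the point is not that the water was overlooked or is shown to be harmful. But the equivalence is asserted for all participants alike, and it does not remove the conflict with item 5.

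Several stronger readings are tempting and are not supported:

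- *That affected participants will swallow 5.4-10.8 L.* Sections A and C allow saliva instead, so this is a ceiling and the floor is 0.
- *That the baseline barium swallow already identifies who must not have water.* Its smallest bolus is larger than the practice volume.
- *That practice is unsupervised.* Caregivers are encouraged to attend training as coaches, and correct use must be shown before the device goes home. Calls are made on each of the first 3 days and then weekly. Participants and caregivers are trained in oral hygiene, wet-voice and temperature checks and upright use, and adverse events are reviewed by the medical officer and the IRBs. These measures teach or monitor everyone; none decides who receives water.

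It may also be said that saliva-only practice would reduce the dose of practice in the most impaired participants. That is a real cost, and the reason for a clearance step and not a ban.

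**Conclusion.** The point holds as a low-cost improvement. The protocol supplies practice water to all participants, including some whom it foresees as unsafe for any intake or tube-fed. It then either contradicts item 5 of Protection against risk or leaves the water without an SLP decision, depending on how item 5 is read.

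Per participant, exposure runs from 0 to 60-120 ml a day, at most 5.4-10.8 L if 3 months is taken as 90 days. How many of the 12-20 planned participants are concerned is not given, so no total can be stated. The documents do not support a claim that harm is expected.

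**What to change.** Two wording changes:

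1. In Swallow Practice, replace the instruction to give water at every practice swallow with water as needed, to match section C.
2. In item 5 of Protection against risk, state that the rule covers practice water. For participants with more than trace aspiration of thin liquid at the baseline barium swallow, or not safe for any intake, the study SLP decides whether 1-2 ml of water may be used. The decision is recorded before the device goes home, and practice is saliva-only until the water is cleared.

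The cost is one recorded decision per such participant, using a clinician and an examination already in the study. Those not cleared may complete fewer than 60 practice swallows a day, since section A expects saliva to run out after about 3. How many fewer cannot be worked out from the documents.
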